9.1.4 Study Visits 2-12

The treatment period is defined as Randomization Study Visit 1 through Study Visit 12. During the study treatment period, any AE associated with the target ulcer and all SAE of any kind will be recorded in the appropriate eCRF. Device deficiencies (DevD) will be recorded in a separate eCRF. The evaluation of all AE is described in Section 12, *Adverse Events*. All weekly visits

must be performed according to the study visit schedule (Section 17), preferably on the same day each week, to conduct all assessments and to assure compliance with treatment. A plus or minus one day visit window will be used for all study visits.

VLU subjects found to have target ulcer closure should continue the compression dressing. Appropriate treatment for DFU subjects found to have target ulcer closure is left to the Investigator's discretion. Appropriate treatment for VLU and DFU subjects, whose target ulcer is ready for and will be surgically closed, is left to the Investigator's discretion. If the Investigator believes the target ulcer is ready for surgical closure, then this procedure should be completed within the same week of the scheduled study visit. The next scheduled visit for subjects with closed target ulcers or subjects that will be surgically closed will be designated as End of Treatment Assessment Visit 14 and should occur in 7 (± 1) days.

All study procedures should occur in the order outlined in the protocol. Study Visits occurring outside the protocol specified visit window should be completed and recorded as a protocol deviation.

1. Subjects will be queried regarding any changes in general health and the use of concomitant medications.
2. Any AE associated with the target ulcer and all SAE of any kind reported since the last assessment will be recorded in the appropriate eCRF. DevD will be recorded in a separate eCRF (see "Section 12, *Adverse Events*" for reporting and evaluating AE). Also, subjects will be queried as to any additional ulcer-related interventions requiring hospital admission, surgical intervention or specialist referral since the last assessment.
3. Assess level of pain from NPWT dressing wear, since the previous study visit, using the VAS.
4. Prior to examination of the ulcer, remove compression bandaging (**for VLU subjects**) and photograph the NPWT topical dressing using the ARANZ Silhouette wound imaging and measurement device.

CONFIDENTIAL DOCUMENT

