- The proportion of subjects with confirmed ulcer closure (achieved by surgical intervention or secondary intention) during the 12-week treatment period. The subject's ulcer closure status (open or closed) will be assessed by the Investigator at each study visit. For purposes of analysis, a closed ulcer is defined as having complete re-epithelialization, without drainage or the need for a dressing; a confirmed closed ulcer is as a closed ulcer with closure status confirmed at a visit 1-week post initial closure. The derivation is as follows:
 - Ulcer Closed=Yes at last attended Study Visit i, Ulcer Closed=Yes at Follow up assessment (visit i+1)

- Confirmed Closure = Yes
- Ulcer Closed= Yes at last attended Study Visit i, Ulcer Closed=No at Follow up assessment (visit i+1)
 - Confirmed Closure = No
- Ulcer Closed=Yes at last attended Study Visit i, Ulcer Closed=missing at Follow up assessment (visit i+1)
 - Confirmed Closure = missing
- Ulcer Closed=No at last attended Study Visit i,
 - Confirmed Closure = No

In cases where the ulcer closure status is missing at a Study Visit, the Last Observation Carried Forward (LOCF) method will be used.

- The time in days to (confirmed) ulcer closure dressing during the 12-week treatment period (with confirmed closure as defined in the previous paragraph). Once a subject has achieved confirmed ulcer closure, either by surgical intervention or secondary intention, the time to healing will be calculated from the date of the randomization visit to the date at which the subject's ulcer was first recorded as closed:

(Date of first Ulcer Closure visit – Date of Randomization (SV1))

For those subjects that withdraw or do not achieve confirmed ulcer closure during the study, the time to complete ulcer closure will be censored at the last visit date attended. The resulting time to complete ulcer closure will be defined as:

(Date of Last Study Visit attended – Date of Randomization (SV1))

Where the censored time to confirmed ulcer closure is greater than 84 days, this will be truncated to 84 days.

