2.3.2 SECONDARY ENDPOINTS

The KEY SECONDARY endpoints are the percentage change in the target ulcer dimensions not assessed as part of the primary endpoint, namely depth and volume. As defined for the primary endpoint, ulcer depth and volume will be measured by the ARANZ Silhouette Device at each visit by the Investigator, and the percentage change in depth over the 12-week treatment period will be derived using the baseline depth and the depth recorded at Study Visit 13. The endpoint will be repeated for ulcer volume.

The remaining secondary endpoints are detailed below:

- The proportion of subjects with confirmed ulcer closure (achieved by surgical intervention or secondary intention) during the 12-week treatment period. The subject's ulcer closure status (open or closed) will be assessed by the Investigator at each study visit. Complete wound closure is defined as complete re-epithelialization, without drainage or the need for a dressing, confirmed at one-week post initial ulcer closure.
When an ulcer closure is initially observed at a weekly treatment visit from Visits 2 to 13, it will be confirmed at the one further study assessment one week later (Visit 14) so that it can be considered as a complete wound closure.
- The time in days to (confirmed) ulcer closure during the 12-week treatment period (with confirmed closure as defined in the previous paragraph). Once a subject has achieved confirmed ulcer closure, either by surgical intervention or secondary intention, the time to healing will be calculated as the number of days between the date of the randomization visit (Study Visit 1) and the date

ST:

9 7 5

Reference:

CE/052/PIC

Customer Code:

0 5

at which ulcer closure first occurred. For those subjects who drop out or who do not achieve the complete wound closure during the 12-week treatment period, the time to complete wound closure will be considered as censored at the last visit date (censored date) of the treatment period or 84 days (i.e. 12 weeks x 7 days), whichever occurs earlier.

- The difference between treatments in the change in subject reported Quality of Life (QoL) during the 12-week treatment period. The Health related Quality of Life (HRQoL) will be assessed using the EQ-5D and Cardiff Wound Impact Schedule (CWIS) validated instruments.

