- Best case: In cases where subjects withdraw from the study prior to the end of the 12-week treatment period (except in cases where the ulcer has closed), the following will be imputed: Confirmed Closure=Yes.

Time to achieve complete closure – Secondary Endpoint:

Once a subject achieves complete ulcer closure as defined above, the time to complete ulcer closure will be calculated as the time interval in number of days between the date of randomization (i.e. Study Visit 1) and the date of the initial observation of the wound ulcer closure. For those subjects who drop out or who do not achieve the complete wound closure during the 12-week treatment period, the time to complete wound closure will be considered being censored at the last visit date (censored date) of the treatment period (i.e. from Study Visits 2 to 13) or 84 days (i.e., 7 days x 12 weeks), whichever occurs earlier. There is no missing data for time to achieve complete closure.

Difference between treatments in Health Related Quality of Life (HRQoL) – Secondary Endpoint:

The EQ-5D and CWIS instruments will be completed at Randomisation (Study Visit 1) and End of treatment. Missing data can occur with the questionnaires due to missed questions or the subject being unwilling to answer. Missed visits may also cause missing data. In cases where questions are skipped, the missing responses will be coded as per the instrument guidelines. Separately, in cases where there are missing individual responses (not complete missing questionnaires) contained on the end of treatment questionnaire, these will be coded as the Last Observation Carried Forward (LOCF) from the baseline questionnaire.

Document Number: 1004313
Document Version: 06

Document Part: 000
Document Status: Released

Ulcer progression parameters – Exploratory Endpoint:

Assessment of change in target ulcer progression parameters over the 12-weeks and comparison between treatments including: Estimation of the types of tissue present on the target ulcer, Presence of Infection/Clinical signs of infection, Condition of peri-wound skin, Need for administration of antibiotics and additional interventions, dressing wear time, pain on removal of dressing and at initiation of, and during, therapy. Missing values and/or visits may occur at these visits if data is not collected or a subject discontinues from the treatment due to ulcer closure or early termination.

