4.3 Derived Data

1. A flag for patient inclusion in the full analysis set. If the patient has received NPWT and has at least one (post-baseline) dressing change assessment then the patient is included in the full analysis set. Otherwise the patient is excluded from the full analysis set.
2. A flag for patient inclusion in the safety population. If the patient has received NPWT, then the patient is included in the safety population. Otherwise the patient is excluded from the safety population.
3. The duration in days between the baseline assessment (Randomization Study Visit 1) and each scheduled Study Visit (2-12) (scheduled every 7 days) and Study Visit 13 or 14.

ST:

9 7 5

Reference:

CE/052/PIC

Customer Code:

0 5

4. The duration in days between the Screening Run-In Visit 1 and Screening Run-In Visit 2.
5. A flag for whether the Screening Run-In Visit 2 occurred 7 (± 1) days after Screening Run-In Visit 1.
6. The duration in days between the baseline assessment (Randomization Study Visit 1) and each scheduled Study Visit (2-12) (scheduled every 7 days) and Study Visit 13/14.
7. A flag for whether study visits occurred weekly after the Randomization Visit as per the protocol. A separate flag should be derived for each study visit.
E.g. Study Visit 2 should occur at 7 (± 1) days after the Randomization Study Visit 1. Study Visit 3 should occur at 14 (± 1) days etc.
8. The duration in days between the Study Visits i and j (where $i \geq 1$ and $j = i + 1$)
9. Patient age (years) defined as: The date of the baseline assessment – date of birth/365.25
10. Patient body mass index defined as: $\text{Weight (kg)} / (\text{Height (cm}/100))^2$
11. Reference wound duration at point of randomisation will be derived as follows:
Date of Target onset date - Date of Randomization Visit 1
12. The (post-screening) study duration (in days) will be derived as follows:
Date of Study Completion - Date of Randomization Visit 1
13. The Screening duration (in days) will be derived as follows (separately for screening, re-screen 1 and re-screen 2 where appropriate):
Date of Run-In Visit 2 - Date of Run-In Visit 1
14. The number of screening periods per subject will be derived as:
No re-screening periods used = 1
A single re-screening period used = 2
Two re-screening periods used = 3

Document Number: 1004313
Document Version: 06

Document Part: 000
Document Status: Released

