15. The change in target ulcer area during the screening period will be derived as (change in depth and volume will be derived using the same method):

$$Area_{Run-In\ 2} - Area_{Run-In\ 1}$$

16. The percentage change in target ulcer area during the screening period will be derived as (percentage change in depth and volume will be derived using the same method):

$$\left(\frac{Area_{Run-In\ 2} - Area_{Run-In\ 1}}{Area_{Run-In\ 1}} \right) \times 100$$

17. Target ulcer area is defined as surface area as measured by the ARANZ Silhouette Device at each study visit by the Investigator. For each study visit, the change in target ulcer area will be derived as (change in depth and volume will be derived using the same method):

$$\text{Change in target ulcer area at Study Visit } n = Area_{SVn} - Area_{SV1}$$

18. For each study visit, the percentage change in target ulcer area will be derived as (percentage change in depth and volume will be derived using the same method):

$$\text{Percentage change in target ulcer area at Study Visit } n = \left(\frac{Area_{SVn} - Area_{SV1}}{Area_{SV1}} \right) \times 100$$

For purposes of the primary analysis, the percentage change in target ulcer area will be derived as using LOCF within the 12-week treatment period. The percentage change in depth and volume will be derived using the same method.

19. The time to achieve confirmed ulcer closure in days will be derived as follows:
- For those subjects that achieve confirmed closure (derived variable 20):
Date of Study Visit where closure is first recorded – Date of Randomization
 - For those subjects that achieve closure but do not achieve confirmation (derived variable 20):
Date of Study Visit where closure is first recorded – Date of Randomization
 - For those subjects that do not achieve closure during the 12-week treatment period or withdraw early, the time to achieve confirmed ulcer closure will be defined as either: Date of last study visit attended – Date of Randomization;
Or 84 days, whichever occurs earlier.

20. Whether confirmed ulcer closure was achieved will be derived as follows:

- Ulcer Closed/Ready for surgical closure=Yes at last attended Study Visit i, Ulcer Closed=Yes at Follow up assessment (Visit 14). Confirmed Closure = Yes
- Ulcer Closed/Ready for surgical closure =Yes at last attended Study Visit i, Ulcer Closed=No at Follow up assessment (Visit 14). Confirmed Closure = No

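### Time to confirmed closure: non-closure times stop at day 84 but confirmed-closure times do not, so a closure first recorded after day 84 has no open-ulcer comparator

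*Protocol*

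**What the plan says.** **Limit on non-closure times.** Protocol 9.4, on time to confirmed closure, states: "Where the censored time to confirmed ulcer closure is greater than 84 days, this will be truncated to 84 days". SAP 2.3.2 censors subjects who drop out or do not close at the last visit of the treatment period or "84 days (i.e. 12 weeks x 7 days), whichever occurs earlier". SAP 2.3.5 repeats this with "the last visit date (censored date) of the treatment period (i.e. from Study Visits 2 to 13) or 84 days". In SAP 4.3 item 19 the limit "Or 84 days, whichever occurs earlier" appears only in the third bullet, for no closure or early withdrawal.

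**No limit on closure times.** SAP 4.3 item 19, first bullet, gives a confirmed closure the time "Date of Study Visit where closure is first recorded – Date of Randomization". Protocol 9.4 uses the same uncapped difference. Item 19's second bullet gives the identical uncapped formula to subjects whose closure is not confirmed.

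**Visit timing.** Protocol 9.1.4 states: "A plus or minus one day visit window will be used for all study visits". SAP 2.2 applies the one-day window to Study Visits 2 to 14, and SAP 4.3 item 7 counts target days from randomization: "Study Visit 3 should occur at 14 (± 1) days etc". SAP 4.6 itself allows 85 days as 12 weeks plus one day. Protocol 9.1.4 also requires out-of-window visits to be completed, although that section covers Visits 2 to 12.

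**Eligible events and analyses.** SAP 2.3.2 accepts a first closure at Visits 2 to 13, and Protocol 9.1.5 sends Visit 13 closures to Visit 14. Protocol 10.3.2 and SAP 4.10 plan a Cox model, Kaplan-Meier plots by treatment and other factors, and a sensitivity analysis that censors early discontinuations at 84 days.

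**The concern.** Events and censored times are measured on different scales at the end of follow-up. Every subject whose ulcer is still open leaves the risk set by day 84, while a closure found at an on-schedule Visit 13 can be dated day 85. Such a closure is compared with nobody whose ulcer is open.

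Two planned outputs are exposed. In the Cox model, which is the treatment comparison for this secondary endpoint, a genuine closure carries essentially no information. In the Kaplan-Meier plots, the tail of the affected arm or stratum can jump to complete closure because of a one-day shift in a visit. The 84-day sensitivity analysis keeps the same asymmetry, so it would not reveal the problem.

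**Working it through.** **1. The plan's figures.** 12 weeks x 7 days = 84, as stated. Visit 13 is the twelfth weekly visit after Study Visit 1 (day 0), so its window is 84 ± 1 = days 83 to 85, which agrees with the 85 days in SAP 4.6.

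**2. Kaplan-Meier, illustration.** Assume 80 subjects in each arm (the planned number randomized), 29 closures per arm by day 84, one more in arm A first recorded on day 85, and all others censored at day 84.
- Day 84: S = 51/80 = 0.6375, so 36.25% closed in each arm.
- Day 85, arm A: one subject at risk, one event. S = 0.6375 x (1 - 1/1) = 0, so 100% closed. The actual proportion is 30/80 = 37.5%.
- With events also capped at 84: arm A ends at 37.5% and arm B at 36.25%.

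This is general. If everyone at risk at the last event time has the event, the last factor is 1 - d/d = 0.

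**3. Effect of item 19, second bullet.** Let one further arm A subject have an unconfirmed closure on day 85, censored at 85 under that bullet. The day-85 risk set is then two: S = 0.6375 x (1 - 1/2) = 0.319, so the curve ends at 68.1% closed. Under Protocol 9.4 the same subject is censored at 84 and the curve ends at 100%.

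**4. Cox model, same illustration.** The lone day-85 event is its own risk set. Its partial-likelihood factor is 1 and its observed minus expected is 0.

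| Closures on day 85 (A vs B) | HR as written | HR with events capped at 84 |
|---|---|---|
| 1 vs 0 (29 earlier closures per arm) | 1.000 | 1.035 |
| 5 vs 0 (28 earlier closures per arm) | 1.000 | 1.18 |

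The second row is deliberately extreme. If both arms have closures on day 85, tie handling leaves a small residual term whose score is zero at HR = 1. The documents name no ties method.

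**5. How often.** The documents give neither closure rates nor the share of visits held a day late. Assume closures spread evenly over the 12 visits from Visit 2 to Visit 13, a closure rate r of 30-60%, and a share q of visits on the +1 day of 10% to one-third. The chance that a subject closes on day 85 is p = r x q / 12.
- Low end: p = 0.30 x 0.10 / 12 = 0.0025. High end: p = 0.60 x (1/3) / 12 = 0.0167.
- Events without an open comparator, 64 per arm: 128p = 0.3 to 2.1, out of 128r = 38 to 77 closures.
- As a share of closures: q/12 = 0.8% to 2.8%.
- Chance that a given arm has at least one: 1 - (1 - p)^64 = 15% to 66%. For at least one of the two arms: 1 - (1 - p)^128 = 27% to 88%.
- With 80 per arm: 160p = 0.4 to 2.7 events, and 33% to 93% for at least one arm.

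These are chances of a day-85 closure. They equal the chance of a curve reaching 100% only if those closures are confirmed and no unconfirmed closer remains at risk.

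**6. Effect on inference.** In simulation (600 trials per scenario, 64 or 80 per arm, same ranges), comparing the rule as written with events capped at 84:
- The mean change in log HR was at most 0.003 with equal closure rates and at most 0.015 with rates 15 points apart.
- The standard error rose by at most about 1%.
- The significance verdict changed in at most about 6% of trials.

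**The case against.** The strongest reply is that the endpoint concerns closure during the 12-week treatment period, which Protocol 9.1.4 ends at Study Visit 12. On that reading a day-85 closure is not an event: the subject is censored at 84 and no curve collapses. This does not stand. SAP 2.3.2 and 2.3.5 both include Visit 13, Protocol 9.1.5 sends Visit 13 closures for confirmation, and the first bullet of item 19 has no period limit. Applied consistently, it would also discard Visit 13 closures on days 83 and 84.

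The remaining replies concern size, and they largely stand. The number of affected events is small. The plan uses Kaplan-Meier for plots only, with no estimate or decision taken from it, and a drop with one or two subjects at risk is easy to see. The percentage closed comes from logistic regression and a chi-square comparison. Protocol 9.1.2 and 9.1.4 steer visits to a fixed weekday, so one-third of visits on the +1 day is an upper-end assumption.

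A reader might infer that all censored times are capped at 84, so that any late closure must send its curve to 100%. SAP item 19, second bullet, does not support that: an unconfirmed closer seen on day 85 can keep the curve below 100%. A reader might also infer that closure is overstated throughout the curve or that the treatment comparison is seriously distorted. Steps 2 and 6 show neither.

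**Conclusion.** The asymmetry is real and the derivation is wrong as written. A confirmed closure first recorded after day 84 has no open-ulcer subject at risk, adds essentially nothing to the hazard ratio, and takes its Kaplan-Meier curve to 100% closed unless an unconfirmed closer is still at risk. Item 19's second bullet separately conflicts with Protocol 9.4 and SAP 2.3.2 and 2.3.5.

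The consequence is limited. Typically 0 to 2 events, about 1-3% of closures, drop out of the Cox comparison, and the plot is wrong only after day 84. Up to day 84 the curve is not inflated; it merely omits the late closures. The primary endpoint and the closure proportion are unaffected. The frequencies rest on assumed closure rates, an even spread of closures over visits and assumed visit shifts; the asymmetry itself rests only on the text. It should be corrected before analysis, because in an open-label trial a repair chosen after seeing the curves would be open to question.

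**What to change.** Apply one end-of-period rule to every time, whether confirmed closure, unconfirmed closure or other censoring. Either:
- cap all times at 84 days, so that a closure first recorded at Study Visit 13 after day 84 is an event at day 84; or
- use nominal visit days for all times, with a cap at 84. The cap is still needed because the last visit attended can be Visit 14.

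State the rule identically in Protocol 9.4, SAP 2.3.2, SAP 2.3.5 and SAP 4.3 item 19, including its second bullet, and use it in the 84-day sensitivity analysis (Protocol 10.3.2, SAP 4.10).

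The cost is about a sentence in each place. Data collection, visits and sample size do not change.

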9.5 HEALTH ECONOMICS/QUALITY OF LIFE

The impact of, and comparison of, trial treatments on subject Quality of Life is included as a secondary study objective. Namely, the difference between treatments in the change in subject reported Quality of Life (QoL) during the 12-week treatment period.

The Health Related Quality of Life (HRQoL) will be assessed using the EQ-5D and CWIS validated instruments. Study subjects will complete both instruments at the Randomization Study Visit 1 and at the End of Treatment period.

Resource use will also be captured and detailed by treatment, including the following: material usage (number of dressing applied and additional materials used), personnel usage (number of personnel, and time, required for dressing change), additional interventions and hospital admissions. Should quantifiable statistical differences be observed in any of the exploratory or safety assessments, a post-hoc health economic analysis will be conducted. This post-hoc analysis will examine the economic implications of the observed differences in resource utilization between the PICO and tNPWT groups by applying existing market prices to the resources utilized and comparing total direct costs between the two groups.

Resource use, as detailed in the previous paragraph, will also separately be detailed by individual tNPWT device.

